6.1 Study treatment

For this study, the term “investigational or study drug” refers to LDK378. All dosages prescribed and dispensed to the patient and all dose changes during the study must be recorded on the Dosage Administration Record eCRF.

LDK378 will be provided and supplied by Novartis. LDK378 is supplied as 150 mg hard gelatin capsules as individual patient supply, packaged in bottles. LDK378 will be dosed on a flat scale of mg/day and not be adjusted to body weight or body surface area.

A complete cycle of treatment is defined as 28 days of once daily treatment of LDK378.

6.1.1 Dosing regimen

[figure not shown]
LDK378 will be administered orally once daily at a dose of 750 mg on a continuous dosing schedule. A complete cycle of treatment is defined as 28 days of once daily treatment of LDK378. The investigator must instruct the patient to take the study drug exactly as prescribed.

- Patients should take LDK378 on an empty stomach (i.e. fast from food and drink, except water) at least 1 hour before or 2 hours after a light meal.
- Each dose of LDK378 should be taken with a glass of water and consumed over as short a time as possible (i.e. not slower than 1 capsule every 2 minutes).
- Patients should be instructed to swallow whole capsules and not to chew or open them.
- If vomiting occurs during the course of treatment, no re-dosing of the patient is allowed before the next scheduled dose.
- Patients should be instructed not to make up missed doses or partial doses (i.e. when the entire dose is not taken as instructed). A missed or partial dose will be defined as a case when the full dose is not taken within 8 hours after the approximate time of the usually daily dosing. That day’s dose (or part remaining dose) should be omitted and the patient should continue treatment with the next scheduled dose on the following day.

Table 6-1 Dose and treatment schedule

Study treatments	Pharmaceutical form and route of administration	Dose	Frequency and/or Regimen
LDK378	Gelatin capsule for oral use	750 mg (5 x 150 mg capsule)	Once daily (28 day cycle)

6.1.2 Guidelines for continuation of treatment

For guidelines for dose modification of treatment, refer to [Section 6.2](#).

6.1.3 Treatment duration

Patients should continue LDK378, and should follow the protocol safety assessments as scheduled, until they experience any of the following:

- Disease progression (radiologically documented according to RECIST 1.1 as assessed by the investigator. Patients who have RECIST-defined PD as assessed by the investigator, but who, in the opinion of the investigator, have evidence of continued clinical benefit from LDK378 may continue to receive the study medication. In such cases, these patients must continue to be followed for safety and efficacy assessments as per the schedule of assessments.
- Unacceptable toxicity that precludes further treatment
- Start of a new anti-cancer therapy
- And/or treatment is discontinued at the discretion of the investigator or patient or the patient is lost to follow-up.

Patients who permanently discontinue the study drug for any reason other than disease progression must, if agreeing to further follow-up, continue efficacy assessments as scheduled in the protocol until the time of confirmed disease progression.

After discontinuing LDK378, further treatment for NSCLC is left to the physician's discretion.

6.1.4 Definition of treatment cycle

A treatment cycle is defined as 28 calendar days from the start of treatment with LDK378 (Day 1, cycle 1) for the purposes of scheduling procedures and evaluations.

6.2 Dose modifications

6.2.1 Dose modification and dose delay

For patients who do not tolerate the protocol-specified dosing schedule, dose adjustments are permitted in order to allow the patient to continue the study treatment. Any changes in LDK378 administration must be recorded on the Dosage Administration Record eCRF.

LDK378 dose modification guidelines are described in [Section 6.2.3](#) and [Table 6-3](#). Any planned variance from these guidelines in view of patient safety must first be discussed with the sponsor unless there is an urgent need for action.

All dose modifications, interruptions or discontinuations must be based on the worst preceding toxicity as graded by the NCI Clinical Toxicity Criteria (NCI-CTCAE version 4.03).

General guidelines for dose modifications for toxicities other than those listed in [Table 6-3](#)

For grade 1 and tolerable grade 2 treatment related toxicities, patients may continue at the current dose of study treatment. For intolerable grade 2 or grade 3 treatment-related toxicities, dosing should be interrupted until at least resolution to grade 1 followed by dose reduction. For any grade 4 toxicity, patients should interrupt study treatment until resolution to at least grade 1, followed by either dose reduction or treatment discontinuation. Treatment with the study drug may subsequently be continued at a reduced dose level if in the opinion of the investigator the patient continues to experience clinical benefit and after discussion with the sponsor.

6.2.2 Treatment interruption and treatment discontinuation

If the administration of LDK378 is temporarily interrupted for reasons other than toxicity, then treatment with LDK378 will be resumed at the same dose. The same applies if the patient experiences an unacceptable toxicity not specifically described in [Table 6-3](#) or [Section 6.2.3](#), provided this toxicity resolved to \leq CTCAE grade 1. If the treatment with LDK378 is withheld due to toxicity, scheduled visits and all assessments (including tumor assessments) will continue to be performed (with the exception of the dosing of the withheld study drug), as described in [Table 7-1](#).

If the treatment with LDK378 is withheld for more than 28 consecutive days (counting from the first day when a dose was missed), due to toxicity, then LDK378 should be permanently discontinued except in cases where the investigator believes the patient continues to derive clinical benefit. In such cases, treatment with LDK378 may be resumed at a lower dose.

If the treatment with LDK378 dosing is withheld for more than 28 consecutive days (counting from the first day when a dose was missed) for reasons other than toxicity, then LDK378 should be permanently discontinued. If dosing was withheld for up to 28 consecutive days for

reasons other than toxicity, then treatment with LDK378 may be resumed at the same dose if the patient is continuing to derive clinical benefit. Patients who discontinue the study due to a study drug related AE or an abnormal laboratory value must be followed as described in [Section 6.2.4](#).

All patients will be followed for safety until 30 days after the last dose of LDK378. Patients whose treatment is temporarily interrupted or permanently discontinued due to an AE or abnormal laboratory value must be followed until resolution or stabilization of the event, whichever comes first, including all study assessments appropriate to monitor the event. Detailed guidelines for follow-up of study drug related AEs or abnormal laboratory values must be followed as described in [Section 6.2.4](#).

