Isolated elevations of any grade	Maintain dose level
Total Bilirubin** (for patients with Gilbert Syndrome these dose modifications apply to changes in direct [conjugated] bilirubin only)	
Grade 1 ($> ULN$ and $\leq 1.5 \times ULN$)	Maintain dose level with LFTs*** monitored as per protocol
Grade 2 (> 1.5 and $\leq 3.0 \times ULN$) with ALT or AST $\leq 3.0 \times ULN$	Omit dose until resolved to \leq Grade 1, then: If resolved in ≤ 7 days, then maintain dose level If resolved in > 7 days, then $\downarrow 1$ dose level

[figure not shown]
Grade 3 (> 3.0 and ≤ 10.0 x ULN) with ALT or AST ≤ 3.0 x ULN	Omit dose until resolved to ≤ Grade 1, then: If resolved in ≤ 7 days, ↓ 1 dose level If resolved in > 7 days discontinue patient from LDK378
Grade 4 (> 10.0 x ULN)	Permanently discontinue patient from LDK378
AST or ALT	
Grade 1 (> ULN and ≤ 3.0 x ULN)	Maintain dose level with LFTs*** monitored per protocol
Grade 2 (> 3.0 and ≤ 5.0 x ULN) without total bilirubin elevation to > 2.0x ULN	Maintain dose level with LFTs*** monitored per protocol
Grade 3 (> 5.0 and ≤ 20.0 x ULN) without total bilirubin elevation to > 2.0 x ULN	Omit dose until resolved to ≤ Grade 1 (or to baseline) then ↓ 1 dose level
Grade 4 (> 20.0 x ULN) without total bilirubin elevation to > 2.0 x ULN	Omit dose until resolved to ≤ Grade 1 (or to baseline) then ↓ 1 dose level
AST or ALT and concurrent Total Bilirubin	
AST or ALT > 3.0 x ULN and total bilirubin > 2.0x ULN in the absence of cholestasis or hemolysis	Permanently discontinue patient from LDK378. Refer to Section 6.2.4.2 for additional follow-up
PANCREATIC	
Amylase and/or lipase elevations (in the absence of clinical symptoms)	
Grade 1 (> ULN and ≤1.5 x ULN)	Maintain dose level
Grade 2 (>1.5 - 2.0 x ULN)	Maintain dose level
Grade ≥3 (> 2.0 x ULN)	Omit dose until resolved to ≤ Grade 1, then ↓ 1 dose level
Note: Withhold LDK378 for acute onset of new or progressive unexplained abdominal symptoms, such as severe pain or vomiting; perform diagnostic procedures (e.g., abdominal CT scan or ultrasound) to exclude pancreatic pathology.	
RENAL	
Serum creatinine	
Grade 1 (>1 and ≤1.5 x baseline; >ULN -1.5 x ULN)	Maintain dose level
Grade 2 (>1.5 and ≤3.0 x baseline; > 1.5 -3.0 x ULN)	Omit dose until resolved to ≤ Grade 1, then: If resolved in ≤ 7 days, then maintain dose level If resolved in > 7 days, then ↓ 1 dose level
Grade 3 (>3.0 x baseline; > 3.0 - 6.0 x ULN)	Omit dose until resolved to ≤ Grade 1, then ↓ 1 dose level

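### For toxicities outside Table 6-3, protocol sections 6.2.1 and 6.2.2 give different restart doses and neither is said to prevail; confirmed pancreatitis is one example

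*Protocol*

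**What the plan says.** Section 6.2.1 carries a block headed "General guidelines for dose modifications for toxicities other than those listed in" Table 6-3. Within it: "For intolerable grade 2 or grade 3 treatment-related toxicities, dosing should be interrupted until at least resolution to grade 1 followed by dose reduction". And: "For any grade 4 toxicity, patients should interrupt study treatment until resolution to at least grade 1, followed by either dose reduction or treatment discontinuation". The block closes by allowing continuation at a reduced level if the investigator sees benefit and the sponsor has been consulted.

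Section 6.2.2 deals first with interruptions for reasons other than toxicity: "then treatment with LDK378 will be resumed at the same dose". It then extends that rule: "The same applies if the patient experiences an unacceptable toxicity not specifically described in" Table 6-3 or section 6.2.3, on condition that the toxicity is back to grade 1 or lower. Later in the same section, a hold for toxicity of more than 28 consecutive days means permanent discontinuation, or a lower dose if the investigator sees continuing benefit.

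On the pancreas, the dose rows of Table 6-3 are headed "Amylase and/or lipase elevations (in the absence of clinical symptoms". At grade 3 or higher they call for a hold until grade 1 or lower and then one level down. For symptoms the table has a note: "Withhold LDK378 for acute onset of new or progressive unexplained abdominal symptoms, such as severe pain or vomiting", followed by diagnostic work-up. Section 6.2.4.3 repeats the hold and work-up, sets enzyme monitoring (including after dosing resumes and after discontinuation for pancreatic toxicity), and refers back to Table 6-3 for dose modification.

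**The concern.** Both sections address toxicities that Table 6-3 does not cover, and both wait for recovery to grade 1. They then send the patient back on different doses. Neither mentions the other on this point. The less cautious section also has the firmer verb: 6.2.2 says treatment *will* be resumed, while 6.2.1 says what *should* be done. A site that follows 6.2.2 to the letter is not deviating from the protocol, yet it gives a higher dose than 6.2.1 intends after the same event.

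What is at stake is mainly patient safety. A secondary matter is that protocol section 10.5.3.5 summarises tolerability through dose reductions and interruptions due to adverse events. The section a site follows therefore also decides whether the patient counts as a reduction or as an interruption only.

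**Working it through.** The plan states no figure on this point, so the check is a comparison of texts plus the dose steps of Table 6-2.

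**1. Where the two rules meet.** Take an event not described in Table 6-3 that has recovered to grade 1 or lower.

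| Event | 6.2.1 | 6.2.2 | Conflict |
|---|---|---|---|
| Treatment-related, grade 3 or intolerable grade 2, held 28 days or less | reduce | same dose | yes |
| Grade 4, any cause, held 28 days or less | reduce or stop | same dose | yes |
| Unrelated grade 2 or 3 | silent | same dose | no |
| Held more than 28 days for toxicity | no same-dose option for the events above | stop, or lower dose | no |

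The conflict is the first two rows. The third shows that the 6.2.2 sentence has a legitimate use of its own.

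**2. Size of the dose difference.** Table 6-2 runs 750, 600, 450, 300 mg in 150 mg steps, with nothing below 300 mg.
- From the starting dose: 6.2.2 gives 750 mg and 6.2.1 gives 750 − 150 = 600 mg. The difference is 150/750 = 20%.
- From the lowest level: 6.2.2 gives 300 mg. Under 6.2.1 a reduction is called for, and Table 6-2 then requires permanent discontinuation.
- Section 6.2.3 does not allow re-escalation after a reduction for toxicity, so whichever reduction is made is lasting.

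**3. Confirmed clinical pancreatitis.** There are two ways to place it.
- *Not described in Table 6-3*, because the rows exclude symptomatic patients. Both 6.2.1 and 6.2.2 then apply and disagree. Under 6.2.2 a confirmed case could restart at the same dose, while a symptom-free enzyme rise of grade 3 or higher drops one level.
- *Described there*, because of the note; the Amendment 3 list of changes also speaks of pancreatitis criteria in the table. The same-dose sentence of 6.2.2 is then switched off. The table still names no restart dose, and the reader must decide whether 6.2.1 fills the gap.

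Either way, no section states the restart dose. Frequency: the Amendment 3 rationale gives less than 1%. If all 124 treated patients were exposed, 124 × 0.01 = 1.24, so the expected count is below about 1.2. It is lower among those still on drug, a number the documents do not give.

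**4. Rough scale of the wider group.** Table 1-1 (phase I study, 750 mg, N = 255) lists grade 3/4 events. Terms touched by neither a Table 6-3 row nor a note are weight decreased 4, headache 3, decreased appetite 2, back pain 1 and dyspepsia 1. Abdominal pain and dyspnea are left out because the pancreatic and pulmonary notes touch them. Hypokalemia is left out because the QTc row mentions it.
- Complete overlap between terms: at least 4 patients, 4/255 = 1.6%.
- No overlap: at most 4 + 3 + 2 + 1 + 1 = 11 patients, 11/255 = 4.3%.

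This range shows scale only. Table 1-1 counts events regardless of drug relationship, omits terms below 10% at all grades, and does not say who was held or restarted.

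**The case against.** The strongest reply is that 6.2.1 is plainly the governing text. It also states that every modification, interruption or discontinuation must rest on the worst grade that came before, which points to a graded rule and away from a restart judged on the recovered grade alone. It is the more specific section, and its closing sentence names only a reduced dose and puts a sponsor discussion before continuation. The list of changes records that its guidelines were added at health authorities' request and that its subtitle was later narrowed to toxicities outside Table 6-3. Other safeguards exist: stopping for unacceptable toxicity (6.1.3), stopping when continuing would be detrimental (7.1.4.1), and the 28-day rule. For the pancreas, section 1.3 names dose adjustment, interruption and discontinuation as the means of managing the risk.

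Most of this stands as evidence of intent, and it lowers the practical risk. It does not settle precedence. Nothing makes the 6.2.2 sentence subject to 6.2.1. The stopping rules do not set a restart dose, and the 28-day rule leaves shorter holds open. The requirement to discuss planned variances with the sponsor follows a sentence about section 6.2.3 and Table 6-3, so it may not reach a toxicity outside both.

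Three stronger readings are tempting and should not be drawn:
- *That the protocol directs patients with pancreatitis back to full dose.* This holds only if pancreatitis is taken as outside Table 6-3 and 6.2.2 is taken to override 6.2.1. The note supports the opposite placing, and 6.2.1 can fill the gap.
- *That pancreatic guidance ends at hold and work-up.* Section 6.2.4.3 goes on to monitoring after resumption or discontinuation and already points to Table 6-3. Only the restart dose is missing.
- *That 6.2.1 imposes a strict duty to reduce, or that Table 1-1 counts the patients affected.* The first is worded as a general guideline. The second ignores relationship and restarts.

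**Conclusion.** The contradiction is in the current text and holds within the limits shown: treatment-related grade 3 or intolerable grade 2, or any grade 4, outside Table 6-3, with a hold of 28 days or less. The consequence for an affected patient is one dose level, or continuing at 300 mg when 6.2.1 with Table 6-2 would stop treatment. How many patients that is cannot be derived from the documents.

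Severity is low to moderate. The Amendment 4 rationale says recruitment is complete, so only patients still on drug are exposed. Sponsor discussion and investigator judgement will often lead to a reduction anyway, and the efficacy conclusions do not change. The conclusion assumes that sites have no instruction outside the two documents that ranks the sections.

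**What to change.** 1. In 6.2.2, add that same-dose resumption does not apply where 6.2.1 calls for reduction or discontinuation, and that 6.2.1 governs in that case. The sentence then keeps its use for unrelated grade 2 or 3 events.
2. In the pancreatic part of Table 6-3, add that confirmed pancreatitis does not restart at the same dose. The minimum is one level down after resolution to grade 1 or lower. The alternative is permanent discontinuation, and that choice belongs to the sponsor's medical team.

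No new cross-reference is needed, because 6.2.4.3 already sends the reader to Table 6-3. The cost is protocol wording only, with no added visits or tests, in a part of the protocol that Amendment 4 was already editing (Table 6-3 and 6.2.4.2). The downside is that some patients will restart at a lower dose that cannot be raised again, which is what 6.2.1 already intends.

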6.2.3 Criteria for LDK378 dose modifications

An LDK378 dose reduction will follow the guidelines described in [Table 6-2](#). For each patient, a maximum of 3 dose reductions will be allowed. All dose reductions will be in 150 mg decrements per reduction. The patient must be discontinued from treatment with LDK378 if further reduction is necessary.

Once the dose of LDK378 has been reduced due to toxicity, it cannot be re-escalated.

Table 6-2 Dose reduction steps for LDK378

LDK378 dose levels	Dose* and schedule
Starting dose level	750 mg qd continuously
Dose level – 1	600 mg qd continuously
Dose level – 2	450 mg qd continuously
Dose level – 3	300 mg qd continuously **

[figure not shown]
*Dose reduction should be based on the worst preceding toxicity as per NCI-CTCAE version 4.03
**Dose reduction below 300 mg/day is not allowed. If a dose reduction below 300 mg/day is required, the patient should be permanently discontinued from LDK378

Guidelines for dose modification and dose interruption of LDK378 are described in [Table 6-3](#).

[figure not shown]
Table 6-3 Criteria for interruption and re-initiation of LDK378 treatment

Dose changes must be recorded on the Dosage Administration Record eCRF.

[figure not shown]
Dose Modifications for LDK378 as specified in Section 6.2.3 .	
Worst toxicity (CTCAE 4.03 Grade)*	Dose Modifications for LDK378
HEMATOLOGICAL	
Neutropenia (ANC)	
Grade 1 (ANC < LLN - $1.5 \times 10^9/L$) Grade 2 (ANC < 1.5 and $\geq 1.0 \times 10^9/L$) Grade 3 (ANC < 1.0 and $\geq 0.5 \times 10^9/L$)	Maintain dose level
Grade 4 (ANC < $0.5 \times 10^9/L$)	Omit dose until resolved to \leq Grade 2, then: If resolved in ≤ 7 days, then maintain dose level If resolved in > 7 days, then $\downarrow 1$ dose level
Febrile neutropenia (ANC < $1.0 \times 10^9/L$, with a single temperature of ≥ 38.3 °C or a sustained temperature of ≥ 38 °C for more than one hour)	Omit dose until clinically resolved and neutropenia \leq Grade 2, then $\downarrow 1$ dose level
Thrombocytopenia	
Grade 1 (PLT < LLN - $75 \times 10^9/L$) Grade 2 (PLT < 75 and $\geq 50 \times 10^9/L$)	Maintain dose level
Grade 3 (PLT < 50 and $\geq 25 \times 10^9/L$)	Omit dose until resolved to \leq Grade 2, then: If resolved in ≤ 7 days, then maintain dose level If resolved in > 7 days, then $\downarrow 1$ dose level
Grade 4 (PLT < $25 \times 10^9/L$)	Omit dose until resolved to \leq Grade 2, then $\downarrow 1$ dose level
HEPATIC	
Alkaline phosphatase and/or GGT	
Isolated elevations of any grade	Maintain dose level
Total Bilirubin** (for patients with Gilbert Syndrome these dose modifications apply to changes in direct [conjugated] bilirubin only)	
Grade 1 ($> ULN$ and $\leq 1.5 \times ULN$)	Maintain dose level with LFTs*** monitored as per protocol
Grade 2 (> 1.5 and $\leq 3.0 \times ULN$) with ALT or AST $\leq 3.0 \times ULN$	Omit dose until resolved to \leq Grade 1, then: If resolved in ≤ 7 days, then maintain dose level If resolved in > 7 days, then $\downarrow 1$ dose level

[figure not shown]
Grade 3 (> 3.0 and ≤ 10.0 x ULN) with ALT or AST ≤ 3.0 x ULN	Omit dose until resolved to ≤ Grade 1, then: If resolved in ≤ 7 days, ↓ 1 dose level If resolved in > 7 days discontinue patient from LDK378
Grade 4 (> 10.0 x ULN)	Permanently discontinue patient from LDK378
AST or ALT	
Grade 1 (> ULN and ≤ 3.0 x ULN)	Maintain dose level with LFTs*** monitored per protocol
Grade 2 (> 3.0 and ≤ 5.0 x ULN) without total bilirubin elevation to > 2.0x ULN	Maintain dose level with LFTs*** monitored per protocol
Grade 3 (> 5.0 and ≤ 20.0 x ULN) without total bilirubin elevation to > 2.0 x ULN	Omit dose until resolved to ≤ Grade 1 (or to baseline) then ↓ 1 dose level
Grade 4 (> 20.0 x ULN) without total bilirubin elevation to > 2.0 x ULN	Omit dose until resolved to ≤ Grade 1 (or to baseline) then ↓ 1 dose level
AST or ALT and concurrent Total Bilirubin	
AST or ALT > 3.0 x ULN and total bilirubin > 2.0x ULN in the absence of cholestasis or hemolysis	Permanently discontinue patient from LDK378. Refer to Section 6.2.4.2 for additional follow-up
PANCREATIC	
Amylase and/or lipase elevations (in the absence of clinical symptoms)	
Grade 1 (> ULN and ≤1.5 x ULN)	Maintain dose level
Grade 2 (>1.5 - 2.0 x ULN)	Maintain dose level
Grade ≥3 (> 2.0 x ULN)	Omit dose until resolved to ≤ Grade 1, then ↓ 1 dose level
Note: Withhold LDK378 for acute onset of new or progressive unexplained abdominal symptoms, such as severe pain or vomiting; perform diagnostic procedures (e.g., abdominal CT scan or ultrasound) to exclude pancreatic pathology.	
RENAL	
Serum creatinine	
Grade 1 (>1 and ≤1.5 x baseline; >ULN -1.5 x ULN)	Maintain dose level
Grade 2 (>1.5 and ≤3.0 x baseline; > 1.5 -3.0 x ULN)	Omit dose until resolved to ≤ Grade 1, then: If resolved in ≤ 7 days, then maintain dose level If resolved in > 7 days, then ↓ 1 dose level
Grade 3 (>3.0 x baseline; > 3.0 - 6.0 x ULN)	Omit dose until resolved to ≤ Grade 1, then ↓ 1 dose level
Grade 4 (> 6.0 x ULN)	Permanently discontinue patient from LDK378

GASTROINTESTINAL	
Diarrhea****	
Grade 1	Maintain dose level but adjust anti-diarrhea treatment
Grade 2 (despite maximal anti-diarrheal medication)	Omit dose until resolved to ≤ Grade 1, then maintain dose level. If diarrhea returns as ≥ Grade 2, then omit dose until resolved to ≤ Grade 1, then ↓ 1 dose level
Grade 3 (despite maximal anti-diarrheal medication)	Omit dose until resolved to ≤ Grade 1, then ↓ 1 dose level
Grade 4 (despite maximal anti-diarrheal medication)	Omit dose until resolved to ≤ Grade 1, then ↓ 1 dose level
Nausea*****	
Grade 1 or 2	Maintain dose level but adjust anti-emetic treatment
Grade 3 (despite standard anti-emetics)	Omit dose until resolved to ≤ Grade 1, then ↓ 1 dose level
Vomiting*****	
Grade 1	Maintain dose level but adjust anti-emetic treatment
Grade 2 (despite standard anti-emetics)	Omit dose until resolved to ≤ Grade 1, then maintain dose level. If vomiting returns as ≥ Grade 2, then omit dose until resolved to ≤ Grade 1, then ↓ 1 dose level.
Grade 3 (despite standard anti-emetics)	Omit dose until resolved to ≤ Grade 1, then ↓ 1 dose level
Grade 4 (despite standard anti-emetics)	Omit dose until resolved to ≤ Grade 1, then ↓ 1 dose level
METABOLIC	
Any Grade hypophosphatemia	Treatment with phosphate supplements as clinically indicated and maintain dose level
Persistent hyperglycemia (glucose >250 mg/dL) despite optimal anti-hyperglycemic therapy	Omit dose until hyperglycemia is adequately controlled, then resume LDK378 at ↓ 1 dose level If adequate hyperglycemic control cannot be achieved with optimal medical management, permanently discontinue patient from LDK378
GENERAL DISORDERS	
Fatigue (asthenia)	
Grade 1 or 2	Maintain dose level
Grade 3	If grade 3 fatigue resolves to Grade 2 in ≤ 7 days, maintain dose level If grade 3 fatigue lasts > 7 days, omit dose until resolved to ≤ Grade 2 and then ↓ dose level
CARDIAC	

Electrocardiogram QT corrected (QTc) interval prolonged	
Grade 1 (QTc 450-480 ms) Grade 2 (QTc 481-500 ms)	Maintain dose level
Grade 3 (QTc ≥ 501 ms- on at least two separate ECGs)	
Omit dose until QTc is less than < 481ms, then ↓ 1 dose level
 
- Assess the quality of the ECG recording and the QT value and repeat if needed
 
Repeat ECG in 24 hours, or less, as clinically indicated; continue monitoring as clinically indicated until QTc < 481 ms
 
In addition:-Determine the serum electrolyte levels (in particular hypokalemia, hypomagnesemia). If abnormal, correct abnormalities before resuming study drug treatment
 
- Review concomitant medication use for drugs with the potential to increase the risk of drug exposure related to QT prolongation
 
[REDACTED]
 
After resumption of dosing: -Repeat ECGs 7 days after dose resumption for all patients who had therapy interrupted due to QTc ≥ 501 ms.

Grade 4 (QTc ≥ 501 or > 60ms change from baseline and Torsades de pointes or polymorphic ventricular tachycardia or signs/symptoms of serious arrhythmia)	Permanently discontinue patient from LDK378
Bradycardia	
Grade 1 or 2	Omit dose until recovery to asymptomatic bradycardia or to a heart rate ≥60 bpm Evaluate concomitant medications known to cause bradycardia, and adjust the dose of LDK378
Grade 3 Grade 4 (in patients taking a concomitant medication also known to cause bradycardia or a medication known to cause hypotension)	Omit dose until recovery to asymptomatic bradycardia or to a heart rate ≥60 bpm If the concomitant medication can be adjusted or discontinued, resume LDK378 at ↓ 1 dose level with frequent monitoring
Grade 4 (in patients who are not taking a concomitant medication also known to cause bradycardia or known to cause hypotension)	Permanently discontinue LDK378

PULMONARY

Notes:

- Withhold LDK378 for acute onset of new or progressive unexplained pulmonary symptoms, such as dyspnea, cough and fever and during diagnostic workup for pneumonitis/ILD.
- During evaluation of potential grade 2, 3, and 4 pneumonitis, if an infectious etiology is confirmed (i.e., pneumonia) and pneumonitis is excluded, then consider resuming LDK378 at current dose level after the pneumonia resolves.

PNEUMONITIS

Any Grade treatment-related ILD/pneumonitis

Permanently discontinue patient from LDK378

[figure not shown]
* Common Terminology Criteria for Adverse Events (CTCAE) version 4.03. All dose modifications should be based on the worst preceding toxicity.

** If Grade 3 or 4 hyperbilirubinemia is due to the indirect (non-conjugated) component only, and hemolysis as the etiology has been ruled out as per institutional guidelines (e.g., review of peripheral blood smear and haptoglobin determination), then ↓ 1 dose level and continue treatment at the discretion of the investigator.

***LFTs include albumin, ALT, AST, total bilirubin (fractionated if total bilirubin > 2.0 x ULN), alkaline phosphatase and GGT

**** Dose modifications apply to patients who experience diarrhea despite appropriate antidiarrheal medication. This medication should be started at the first sign of abdominal cramping, loose stools or overt diarrhea (see [Section 6.2.4.4](#))

***** Dose modifications apply to patients who experience nausea and/or vomiting despite appropriate antiemetic medication. This medication should be started at the first sign of nausea and/or vomiting (see [Section 6.2.4.5](#))

